5.5.3. Additional Safety Assessments

5.5.3.1. Clinical Laboratory Tests

Definition: A post-baseline abnormality (based on criteria defined in [Table 6](#)) will be considered treatment emergent if it is worse than the baseline abnormality and assessed after the initial administration of study intervention (on Day 1) and no later than EOT plus 3 days. If the baseline abnormality information is missing, the abnormality is always considered treatment emergent. If the post-baseline value is above the upper limit and the baseline value is below the upper limit, then the post-baseline abnormality will be considered treatment emergent. The same applies to the post-baseline value being below the lower limit and the baseline value being above the lower limit. However, a post-baseline abnormality that is in the same category of abnormality already existing at baseline will not be counted as treatment emergent. For example, if a participant already has “marked abnormality” in hemoglobin at the (re-)baseline, (s)he will have TE “alert abnormality” when at least one of the post-baseline values meets the hemoglobin alert criteria. But (s)he will not have TE “marked abnormality” regardless of the post-baseline values, and this participant will be excluded from the denominator of TE marked abnormality in hemoglobin.

For each analysis set, the worst post-baseline abnormal (for both above or below the normal range) result of a parameter is considered. Unscheduled visit results are also included.

Table 6: Definition of Abnormalities for Hematology and Chemistry Test

| Parameter (SI unit) | LL Marked | LLL Alert | HH Marked | HHH Alert |
|---|--------------|--------------|------------------------|------------------------|
| Hemoglobin (g/L) baseline within ULN | < 100 | < 80 | > 20 above ULN | > 40 above ULN |
| baseline above ULN | < 100 | < 80 | > 20 above baseline | > 40 above baseline |
| Hematocrit (L/L) males | < 0.32 | < 0.20 | > 0.60 | > 0.65 |
| females | < 0.28 | < 0.20 | > 0.55 | > 0.65 |
| Platelets (10 ⁹ /L) | < 75 | < 50 | > 600 | > 999 |
| Leucocytes (10 ⁹ /L) | < 3 | < 2 | > 20 | > 100 |
| Neutrophils (10 ⁹ /L) | < 1.5 | < 1.0 | - | - |
| Eosinophils (10 ⁹ /L) | - | - | > 5 | - |
| Lymphocytes (10 ⁹ /L) | < 0.8 | < 0.5 | > 4 | > 20 |
| ALT | - | - | > 3 ULN | > 5 ULN |
| AST | - | - | > 3 ULN | > 5 ULN |
| Alkaline Phosphatase | - | - | > 2.5 ULN | > 5 ULN |
| Direct Bilirubin | - | - | > 2 ULN | > 5 ULN |
| Total Bilirubin | - | - | > 2 ULN | > 5 ULN |
| Creatinine baseline within ULN | - | - | > 1.5 ULN | > 3 ULN |
| baseline above ULN | - | - | > 1.5 baseline | > 3 baseline |
| Glucose (mmol/L) | < 3 | < 2.2 | > 8.9 | > 13.9 |
| Sodium (mmol/L) | - | < 130 | > 150 | > 155 |
| Potassium (mmol/L) | < 3.2 | < 3 | > 5.5 | > 6 |
| Urea (mmol/L) | - | - | > 2.5 ULN | > 5 ULN |
| Albumin | < 30 | < 20 | - | - |
| Creatinine Clearance/eGFR (mL/min) | < 60 | < 30 | - | - |
| BUN | - | - | > 2.5 ULN | > 5 ULN |

ULN = upper limit of the laboratory normal range. This table is based on Actelion OTH-000005 version 09.

Laboratory parameters collected in a study level are not always the same across studies. Some of the parameters listed above might not be applicable in certain studies.

Population: All participants included in the STS (A302+A303) and OLS

Study Intervention: Selexipag

Outcome measures: Treatment emergent markedly abnormal laboratory values.

Summary method(s) for outcome measure:

- Number and percentage of participants with treatment-emergent markedly abnormal laboratory values will be presented by treatment group over time.
- The treatment-emergent laboratory abnormalities will also be reported for subgroups by PAH medication at baseline - group 1 (defined in Section 5.6.8).
- Descriptive summary statistics by visit are displayed for observed values and absolute changes from baseline to each visit for hematology and blood chemistry laboratory tests from the central laboratory. Separate tables for STS and OLS will be produced.

- The descriptive summaries and changes from baseline as specified above will also be reported for subgroups by PAH medication at baseline - group 1 (defined in Section 5.6.8). Separate tables for STS and OLS will be produced.

If a parameter is not analyzed in A302 or A303, it will be reported only in the study that is applicable, e.g., lymphocytes is collected in A302 only, it will be summarized/listed under STS (all from A302) and empty in OLS.

Separate listings of markedly abnormal laboratory values (by group of parameters) will be provided for STS (A302+A303) and OLS.

Additionally, listings of all available laboratory values (by group of parameters) will be provided for STS (A302 + A303) and OLS, separately. The available laboratory parameters are shown in Table 7 below.

Table 7: Laboratory parameters

| Parameter (SI unit) | |
|---|---|
| 1. ALT (IU/L) | 15. Glucose (mmol/L) |
| 2. Albumin (g/L) | 16. Hematocrit (L/L) |
| 3. Alkaline Phosphatase (IU/L) | 17. Hemoglobin (g/L) |
| 4. AST (IU/L) | 18. Leucocytes ($10^9/L$) |
| 5. Basophils ($10^9/L$) | 19. Lymphocytes ($10^9/L$) |
| 6. Basophils/Leukocytes (%) | 20. Lymphocytes/Leucocytes (%) |
| 7. Total Bilirubin ($\mu\text{mol/L}$) | 21. Monocytes ($10^9/L$) |
| 8. Direct Bilirubin ($\mu\text{mol/L}$) | 22. Monocytes/Leucocytes (%) |
| 9. Blood Urea Nitrogen (mmol/L) | 23. N-Terminal ProB-type Natriuretic Peptide (ng/L) |
| 10. Creatinine ($\mu\text{mol/L}$) | 24. Neutrophils ($10^9/L$) |
| 11. Creatinine Clearance (mL/min) | 25. Neutrophils/Leucocytes (%) |
| 12. Eosinophils ($10^9/L$) | 26. Platelets ($10^9/L$) |
| 13. Eosinophils/ Leucocytes (%) | 27. Potassium (mmol/L) |
| 14. Erythrocytes ($10^{12}/L$) | 28. Sodium (mmol/L) |

5.5.3.1.1. Abnormalities in liver function test results

Additional analyses for TE abnormalities in liver function tests will be performed.

Definition: Additional abnormalities in liver function tests are defined as follows (the “and” conditions do not require concomitant values):

- AST > 3 × ULN or ALT > 3 × ULN
- AST > 5 × ULN or ALT > 5 × ULN
- AST > 8 × ULN or ALT > 8 × ULN
- ALT > 3 × ULN and total bilirubin > 2 × ULN
- (AST > 3 × ULN or ALT > 3 × ULN) and total bilirubin > 2 × ULN.

Abnormality criteria will be applied to baseline and post-baseline values.

Population: All participants included in the STS (A302+A303) and OLS

Study Intervention: Selexipag

Outcome measures: Abnormalities in liver function tests.

Summary method(s) for outcome measure:

- Number and percentage of participants with TE abnormalities
- Abnormalities in liver function tests will also be reported for subgroups by PAH medication at baseline - group 1 (defined in Section 5.6.8).
- A listing and an eDISH plot will be produced to show possible cases as specified in the 4th and 5th abnormalities numbered items. Separate listings and eDISH plots will be produced for STS and OLS.

Separate listings of markedly abnormal values of ALT and AST will be provided for STS (A302+A303) and OLS.

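### The combined ALT/AST and bilirubin criteria have no time link, so elevations years apart count as one possible case and no concurrent count is planned

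*SAP*

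**What the plan says.** SAP section 5.5.3.1.1 defines five additional liver abnormalities. The fourth is "ALT > 3 × ULN and total bilirubin > 2 × ULN", and the fifth allows AST in place of ALT. The section states that the joint "conditions do not require concomitant values". The outputs are:

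- "Number and percentage of participants with TE abnormalities", reported for the open-label treated set (OLS) and the selexipag-treated set (STS), and by PAH-medication subgroup;
- a listing and plot: "A listing and an eDISH plot will be produced to show possible cases as specified in the 4th and 5th abnormalities numbered items".

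The parent section, SAP 5.5.3.1, sets the general laboratory rules. For each analysis set, "the worst post-baseline abnormal (for both above or below the normal range) result of a parameter is considered". On extra samples it says "Unscheduled visit results are also included". The treatment-emergent window closes "no later than EOT plus 3 days", so it spans the whole time on treatment. Neither section gives a maximum interval between the two values, a same-sample count or an exposure-adjusted rate for these criteria.

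**The concern.** A joint elevation of aminotransferase and bilirubin is informative mainly because the two move together. Without a time link, the fourth and fifth criteria also collect participants who had one isolated elevation of each kind, perhaps years apart. The count cannot separate these two situations, and neither can a plot that places each participant by worst values.

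The window is long enough for this to matter. A303 enrolment ran from 7 July 2010 to 2 September 2014 (SAP 1.2), and the protocol's COVID-19 appendix is dated 16 June 2020, 9.9 years after the first enrolment. The STS adds selexipag exposure from A302, with a median of 18.8 months (SAP 1). Protocol 3.9.1.2.2 and 3.10.3.1 require chemistry at every visit, with visits six months apart from Visit 5.

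What is at stake is comparison. SAP section 4 puts OLS and STS columns side by side although their windows differ in length, and the liver criteria are also split by PAH medication. For adverse events the SAP allows for unequal exposure, with exposure-adjusted incidence rates (5.5.2.1) and annualized rates for events of special interest (5.5.2.2). It makes no such allowance here, where chance pairs grow faster than exposure.

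**Working it through.** The plan states no liver case count or rate, so there is no figure of its own to reproduce. The check asks how chance pairs behave under each rule.

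**Inputs from the documents**
- Group sizes (SAP section 4): OLS 330 + 379 = 709; STS 574 + 379 = 953. Treated with selexipag only in A302: 574 − 330 = 244.
- Scheduled post-baseline draws on the titration schedule (protocol 3.10): Weeks 4, 8 and 16 and Month 6, then two a year. That gives 5 by year 1, 13 by year 5 and 23 by year 10.

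**Assumptions, not in the documents**
- Per-draw probabilities pA = 0.3% (ALT/AST > 3 × ULN) and pB = 1% (bilirubin > 2 × ULN), independent of each other and across draws, with no true joint event.
- m = 13 draws for the 709 and m = 6 for the 244. Six is what the A303 titration schedule would give by 18.8 months; the A302 schedule is not in the documents.

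**Formulas**
- Any-time rule: N × [1 − (1 − pA)^m] × [1 − (1 − pB)^m], about N·m²·pA·pB for small probabilities.
- Same-sample rule: N × [1 − (1 − pA·pB)^m], about N·m·pA·pB.
- The ratio of the two is close to m.

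**Any-time rule**
- 709 × 0.0383 × 0.1225 = 3.33
- 244 × 0.0179 × 0.0585 = 0.26
- Total 3.6

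**Same-sample rule**, with pA·pB = 0.00003
- 709 × [1 − (1 − 0.00003)^13] = 0.28
- 244 × [1 − (1 − 0.00003)^6] = 0.04
- Total 0.3

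**Range.** With the same draw counts, pA = 0.2% and pB = 0.5% give 1.2 against 0.1. With pA = 0.5% and pB = 2% the result is 11.2 against 1.1.

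**Growth with follow-up** (N = 709, pA = 0.3%, pB = 1%, everyone assumed to reach the stated number of draws)

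| Draws | Any-time | Same sample |
|---|---|---|
| 5 | 0.52 | 0.11 |
| 13 | 3.33 | 0.28 |
| 23 | 9.77 | 0.49 |

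From 5 to 13 draws the any-time count rises 6.4-fold and the same-sample count 2.6-fold. The approximations predict (13/5)² = 6.8 and 13/5 = 2.6.

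**Robustness.** A simulation let each participant's risk vary (gamma, coefficient of variation 1.5 for each test), with N = 953, pA = 0.5% and pB = 1%. It gave 6.1 against 0.56 at 13 draws and 15.6 against 1.2 at 23 draws. The pattern is the same. The 23-draw results are upper bounds, because few participants can have been treated that long.

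**The case against.** The strongest defence is that this is an openly stated, sensitive screen. The SAP says the values need not coincide and calls the results possible cases. With six-monthly sampling, a strict time link could miss a genuine case whose two elevations fell on different draws. Timing can also be checked by hand: 5.5.3.1.1 lists the participants meeting the two criteria, 5.5.3.1 lists all available laboratory values, and there may be only a handful of such participants. The SAP's version history refers to separate data presentation specifications, which are not available here and could already contain an interval column or plot symbol. No hypothesis testing is planned, and any crude ever-event percentage rises with follow-up, including the first three liver criteria.

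Most of this stands, and it is why the screen should be kept. It does not answer the point. Listings leave the reported count, percentage and plot as they are, and sorting cases after seeing them is weaker than a rule set beforehand. A time link would not remove growth with exposure, but chance pairs would then grow roughly in proportion to draws rather than with their square.

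A reader might infer more than the documents support:

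- **A large excess.** Giving all 953 STS participants 20 draws yields 953 × 0.0583 × 0.1821 = 10.1 chance cases against 0.57, about 18-fold. That does not fit the population. The 244 never treated in A303 had only A302 exposure. Ex-placebo participants count only from A303, and the last person enrolled had at most 7.06 years to the date of SAP version 2, about 17 scheduled draws. Treatment also ends when selexipag becomes commercially available in the participant's country.
- **Inflation of the reported count by that factor.** The ratio compares chance pairs with chance pairs and mostly reflects the assumed number of draws. The reported count would also contain any true concurrent cases.
- **That this is the study's main signal for serious liver injury.** SAP 5.5.3.1.1 calls these additional analyses, the protocol endpoints (3.8.2) are adverse-event endpoints, and the special-interest list in SAP 6.8 has no hepatic category.

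**Conclusion.** The point holds as a modest weakness in reporting. The fourth and fifth criteria pool concurrent elevations with elevations any distance apart on treatment, and no planned count separates them. Crude percentages across columns and subgroups with unequal exposure are therefore hard to compare.

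The direction follows from the rule itself. The size does not, because the documents give no event rates. Under the stated assumptions it is about 3.6 chance cases against 0.3, and about 1.2 to 11.2 against 0.1 to 1.1 over the range tried. The true excess may be only a few participants. The calculation rests on independent elevations, on assumed draw counts and on scheduled draws only. Persistent elevations would lower the effective number of draws, and unscheduled samples would raise it. No data are lost, and the rule is defensible as a screen if a linked count stands beside it.

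**What to change.** In SAP 5.5.3.1.1:

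- Keep the fourth and fifth criteria unchanged as the sensitive screen.
- Add the same two criteria with a prespecified time link, for example bilirubin on the same day as, or within 30 days after, the qualifying ALT/AST value. The exact interval is the sponsor's choice; it should be fixed before the data are reviewed.
- Show the interval between the two qualifying values in the listing of possible cases.
- Mark concurrent cases with a separate symbol on the eDISH plots.

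The cost is two extra table rows, one listing column and a plot symbol, all from data already collected. The downside is that with six-monthly sampling the linked count alone could miss cases, so both counts should be reported together.

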5.5.3.2. Vital Signs

Definition: Vital signs, including blood pressure (systolic and diastolic) and heart rate, is recorded on the Vital Signs page of the A302/A303 CRF. Treatment-emergent vital signs abnormalities are defined as any new vital signs abnormalities reported after baseline (Section 5.1.5) in A302/ A303 and up to EOT plus 3 days. Markedly abnormal vital signs during intervention are defined in Table 8.

Table 8: Markedly Abnormal Vital Signs

| Vital Sign | Criteria | |
|--------------------------|--|--|
| Systolic blood pressure | SBP < 90 mmHg | Or all four notable criteria fulfilled |
| | Decrease of > 40 mmHg in SBP from baseline | |
| Diastolic blood pressure | DBP < 50mmHg | |
| | Decrease of > 20 mmHg in DBP from baseline | |

Population: All participants included in the STS (A302+A303) and OLS

Study Intervention: Selexipag

Outcome measures: Continuous vital sign parameters.

Summary method(s) for outcome measure:

- Continuous vital sign parameters will be summarized at each visit with descriptive statistics.
- Change from baseline to each visit will be summarized with descriptive statistics.
- Incidence of treatment-emergent markedly abnormal vital signs during study intervention for participants who had a baseline assessment and at least 1 post baseline assessment for that vital sign, at each visit and overall at any time.

A listing of participants with treatment-emergent markedly abnormal vital signs will be presented, along with a listing of all vital sign measurements. The listings will be presented separately for STS and OLS.

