5.1.5. Baseline definition

5.1.5.1. For Treated Set - OL

Baseline is defined as the last observation prior to or on the respective Study Day 1 (Section 5.1.3.1) of selexipag treatment start in A303.

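### The vital-signs incidence counts only new abnormalities but keeps participants already below SBP 90 or DBP 50 mmHg at baseline in the denominator, unlike the laboratory rule

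*SAP*

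**What the plan says.** Numerator. SAP 5.5.3.2: "Treatment-emergent vital signs abnormalities are defined as any new vital signs abnormalities reported after baseline", counted up to three days after end of treatment. The word new is not defined further.

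Denominator. The same section reports the incidence, by visit and overall, "for participants who had a baseline assessment and at least 1 post baseline assessment for that vital sign". It removes nobody for being abnormal at baseline.

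Criteria. Table 8 has an absolute limit for each pressure (SBP < 90 mmHg, DBP < 50 mmHg) and a change criterion for each: "Decrease of > 40 mmHg in SBP from baseline" and "Decrease of > 20 mmHg in DBP from baseline". A side entry offers fulfilment of all four as an alternative. The table does not say whether the two rows under one pressure are alternatives or are both required.

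Laboratory rule. SAP 5.5.3.1 says that "a post-baseline abnormality that is in the same category of abnormality already existing at baseline will not be counted as treatment emergent". In its worked example of a participant who starts with a marked hemoglobin abnormality, "this participant will be excluded from the denominator of TE marked abnormality in hemoglobin".

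Protocol 5.2.2.3 asks for the percentage of patients beyond clinically important limits and sets no denominator. SAP Appendix 2, on changes to protocol-planned analyses, does not mention the point.

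**The concern.** A proportion of new cases is read as a risk, so its denominator should hold people who could become cases. A participant whose baseline SBP is already below 90 mmHg cannot newly fall below 90 if new means absent at baseline, but is still counted as assessed. The percentage is pulled down by the share of such participants.

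The SAP recognises this for laboratory values and resolves it by exclusion. Two adjacent sections therefore give treatment-emergent percentages of the same kind on different footings, without explanation. Safety and tolerability are the study's only objective, and this table is its summary of measured low blood pressure.

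**Working it through.** **Inputs from the documents.** Set sizes, SAP Section 4: ex-selexipag 330, ex-placebo 379, total A303 709, selexipag in A302 574, all 953. They add up: 330 + 379 = 709 and 574 + 379 = 953. These are upper bounds for the vital-signs denominators, which also need a baseline and a later value. The plan states no vital-signs incidence, so there is no figure to reproduce.

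**Assumptions.** p0, the share meeting the absolute limit at baseline: 2% to 10%. p, the incidence of a new abnormality among those not meeting it at baseline: 5% to 20%. Neither is in the documents.

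**Formula.** With N assessed, B = p0 × N abnormal at baseline, and x = p × (N − B) new cases:

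- SAP 5.5.3.2 reports x / N = p × (1 − p0).
- The laboratory-style rule reports x / (N − B) = p.
- The relative understatement is p0.

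| Assumed p0 | p = 5% shown as | p = 10% shown as | p = 20% shown as | Kept in denominator, of 709 | of 953 |
|---|---|---|---|---|---|
| 2% | 4.9% | 9.8% | 19.6% | 14 | 19 |
| 5% | 4.75% | 9.5% | 19.0% | 35 | 48 |
| 10% | 4.5% | 9.0% | 18.0% | 71 | 95 |

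**Can p0 be taken as zero?** Protocol 4.3.2.4 lists low systemic arterial pressure among the events expected in this disease, so some participants starting low is plausible. If the true prevalence were only 1%, the chance of having none would be 0.99^709 = 0.08% in the open-label set and 0.99^953 = 0.007% in the selexipag-treated set.

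**Dependence on the reading of Table 8.** The change criteria cannot be met at baseline, so they are not diluted, and neither is the all-four composite. If the limit and the change under one pressure had to be met together, nobody could qualify at baseline and the effect would be zero. The side entry speaks of four criteria, one per row, which favours separate criteria but does not settle it.

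**Dependence on new.** If a low value after an intervening normal one counted as new, and a share q of baseline-abnormal participants had one, the reported figure would be p × (1 − p0) + q × p0. With p = 10% and p0 = 5%, this is 9.5% at q = 0, 10.0% at q = 10% and 10.5% at q = 20%. The direction then turns on whether q is below or above p.

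**The case against.** **Two definitions are open.** The understatement needs separate Table 8 rows and a strict meaning of new, and the SAP states neither. This stands: the effect is conditional. It also means that two programmers could produce different percentages from the same data, so the text needs settling either way.

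**The denominator is a legitimate convention.** New cases over all assessed is a valid crude proportion, and SAP 5.5.2.1 divides adverse events by all participants. But a participant with an ongoing adverse event can still contribute by worsening, which Protocol 4.1 records as a new event. A participant already below an absolute limit cannot contribute on that criterion. The closer comparison is the laboratory section, which excludes.

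**The effect is small and the study descriptive.** True: at p = 10% the shift is 0.2 to 1.0 percentage points over the assumed range, and no test depends on it. By-visit summaries and listings show the raw values, but they do not correct the reported percentage.

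**Two stronger readings are not supported.** A reader might infer that hypotension as an adverse event of special interest is understated. It is not: that category (SAP 5.5.2.2 and Appendix 8) rests on reported events and does not use this denominator.

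A reader might also infer that the ex-selexipag column is diluted more than the ex-placebo column, because its baseline follows exposure in A302: "Baseline is defined as the last observation prior to or on the respective Study Day 1 (Section 5.1.3.1) of selexipag treatment start in A303". Unequal dilution is possible. With p = 10% in both groups, p0 of 10% against 5% would show 9.0% against 9.5%. But no baseline prevalence by group is given. Protocol 1.3.2.1 reports no clinically relevant blood pressure changes in healthy subjects, and 1.3.2.2 reports no change to end of treatment in either arm in patients. Both groups may take other PAH therapies, and some ex-selexipag participants had interruptions of three days or more between studies. The documents establish neither direction nor size.

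**Conclusion.** The point holds in a limited form. On the more natural reading of Table 8, and with new meaning not met at baseline, the rule dilutes the incidence of markedly low measured blood pressure on the SBP < 90 and DBP < 50 mmHg criteria by exactly the baseline-abnormal share. That share is unknown. For assumed values of 2% to 10%, the relative understatement is 2% to 10%. It is zero if limit and change must be met together, and of uncertain sign if recurrence after normal values counts as new. The unexplained departure from the SAP's own laboratory rule does not depend on these assumptions. The effect is modest, but it touches a reported safety percentage and is easily removed.

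**What to change.** In SAP 5.5.3.2:

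- State that each Table 8 criterion is assessed separately, or state how the criteria combine.
- Define new as not met at the baseline of the analysis set concerned.
- For SBP < 90 and for DBP < 50 mmHg, exclude participants meeting that criterion at baseline from its numerator and denominator, per visit and overall, as in 5.5.3.1.
- Keep all assessed participants for the two change-from-baseline criteria.
- Exclude nobody from the all-four composite, since it cannot be met at baseline.
- Show the number excluded for each criterion and column. This would also show whether the ex-selexipag and ex-placebo columns differ at baseline.

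The cost is a few sentences and a denominator flag per absolute criterion, with no new data. The drawbacks are denominators that differ between Table 8 rows and slightly less favourable figures.
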